6.1 Study treatment

INC280 will be considered as the investigational treatment or the “study drug” for this study.

6.1.1 Dosing regimen

INC280 will be dosed on a flat scale of mg/day and not individually adjusted by body weight or body surface area. Hard gelatin capsules at strength of 50 mg, and film-coated tablets at dosage strengths of 50 mg and 200 mg are available. Tablets at 150 mg strength may be also provided according to local regulations when available.

During the Dose Expansion Part, the INC280 formulation may be changed from capsule to tablet upon its availability.

6.1.1.1 Instructions for administration of INC280

INC280 will be administered orally and continuously on bid dosing schedule. A treatment cycle is defined as 21 days in Dose-Determining and Dose Expansion parts.

Except on the days of full PK profiles sampling, patients should be instructed to take their dose at approximately the same time each day. The second (evening) dose should be taken 12 (± 2) hours apart from first morning dose. Patients will self-administer the study medication with a glass of water at about the same time every day. Patients will consume another glass of water approximately 2 hours after dosing. INC280 should be administered in the fasted state, at least 1 hour before or 2 hours after a meal. During fasting period, patients can freely drink water. Patients should avoid consumption of Seville orange (and juice), grapefruit or grapefruit juice and start fruits during the treatment. On the days when PK blood samples are to be collected (Section 7.2.3), patients will be instructed to hold their dose of INC280 until arrival at the study center. The administration of study treatment will be supervised by the study personnel. The same dietary restrictions for dosing will be in place on days with PK sampling.

- If vomiting occurs, no attempt should be made to replace the vomited dose. If any episodes of vomiting occurred within the first 4 hours of INC280 dosing, on PK sampling days, exact time of vomiting should be recorded on the appropriate electronic Case Report Form (eCRF) besides the AE eCRF.
- A missed dose is defined as any time point when a patient forgets to take INC280 within 8 hours after the planned time of dosing or if a patient forgets to take his/her dose for that day. In such cases, the dose should be omitted and the patient should continue treatment with the next scheduled dose.
- On days when PK [REDACTED] blood samples are to be collected after Cycle 2, study drug will be administered at the site in the morning.

During the entire duration of treatment with INC280, the patient is recommended to use precautionary measures against ultraviolet exposure (e.g., use of sunscreen, protective clothing, avoid sunbathing or using a sunlamp or tanning bed).

6.1.2 Treatment duration

All patients will be treated with INC280 administered orally, beginning on Cycle1 Day1. Each cycle will have 21 days. All patients will continue to receive INC280 until disease progression or unacceptable toxicity occurs, withdrawal of consent, or discontinuation for any other reason.

6.2 Dose modifications guidelines

6.2.1 Starting dose rationale

The selection of the oral dosing schedule had been discussed above [Section 2.3](#).

6.2.2 Implementation of dose decision analysis

To implement dose determination for Dose Expansion Part, the available toxicity information (including AEs and laboratory abnormalities that are not qualifying AEs), the recommendations from the BLRM, and the available PK [REDACTED] information will all be evaluated by the Investigators and Novartis study personnel (including the study physician and statistician) during dose decision meeting by teleconference. Drug administration at Dose Expansion Part may not proceed until the investigator receives written confirmation from Novartis indicating that the results of the Dose-Determining Part were evaluated and that it is permissible to proceed to the Dose Expansion Part.

For safety analysis: The tolerability of INC280 will be evaluated by the BLRM based on the incidence of qualifying adverse events during the first 28 days treatment for which relationship to study treatment cannot be ruled out (see [Table 6-2](#) and [Section 10.5.3.3](#) for details). The BLRM will recommend the highest dose which is estimated to be tolerable (as per the Escalation with Overdose Control (EWOC) criteria). The EWOC criteria mandate that any dose that is estimated to have 25% or more chance to be excessively toxic ($\geq 33\%$ qualified AE-rate) must not be used until more data is available. At time of the analyses, BLRM will include all available safety data for INC280 from this study and external trials. See [Section 10.5.3.3](#) for details.

For PK analysis: Mean ratio of INC280 systemic clearance will be calculated based on the data from HCC patients in the Dose-Determining Part and pooled historical data from cancer patients who had normal liver function (NCI-ODWG criteria) ([Patel et al 2004](#)). If INC280 exposure in Dose-Determining Part is comparable to the historical data, as indicated by mean ratio of the systemic clearance, Expansion Part dose will be recommended as recommended phase 2 dose (RP2D). If INC280 exposure at Dose-Determining Part dose is higher, Expansion Part dose as per PK analysis will be the RP2D proportionally reduced by the decreased mean ratio. If INC280 exposure in lead-in Dose-Determining Part is lower, Expansion Part dose as per PK analysis will be the RP2D proportionally increased by the increased mean ratio taking into consideration the toxicity and feasibility. For details of PK analysis and PK specific criteria for choosing a dose, please refer to [Section 10.5.4.1](#).

The rules for dose recommendation for the Dose Expansion Part will be followed as listed in [Table 6-1](#). The Expansion Part dose can be the same, lower or higher than the Dose-Determining Part dose.

Table 6-1 Rules for dose recommendation for the Dose Expansion Part

Consideration of both safety and PK data based on the following scenarios		Recommended Expansion Part Dose
Safety	INC280 exposure (PK profile)	
Tolerable	Comparable	RP2D/MTD/maximum tested dose that is determined to be safe, from dose escalation studies CINC280X1101, CINC280X2102 and/or INCB28060-101
	Increase in exposure	Proportional reduction of RP2D; if the reduced dose is lower than the Dose-Determining Part dose, use the Dose-Determining Part dose for Dose Expansion Part.
	Decrease in exposure	Proportional increase of RP2D by taking into consideration the toxicity and feasibility.
Intolerable	Comparable	Highest dose recommended by BLRM safety analysis
	Increase in exposure	The lower of the dose following recommendation from PK and safety analysis: - Proportional reduction of the Dose-Determining Part dose - Highest dose recommended by BLRM safety analysis
	Decrease in exposure	Highest dose recommended by BLRM safety analysis

6.2.3 Adverse events criteria for dose decision analysis

As mentioned in [Section 4.1](#) and [Section 10.5.3.3](#), a two-parameter BLRM will be used for the safety analysis. This safety analysis (to be performed during the dose decision analysis after the Dose-Determining Part as well as to confirm the Expansion Part dose) will be based on data (occurrence/ absence) of certain AEs within 28 days treatment. The qualifying AEs are defined as an adverse event or abnormal laboratory value that is assessed by the investigator as related to therapy with INC280 and unrelated to disease progression, intercurrent illness, or concomitant medications and meets any of the criteria in [Table 6-2](#). The qualifying AEs will be considered in the safety analysis

Table 6-2 Criteria for qualifying AEs to be considered for the dose decision analysis

Toxicity	Any of the following criteria:
Hematology	Any grade 3 hematologic toxicity, lasting for > 7 consecutive days Grade 3 thrombocytopenia with bleeding Any grade 4 hematologic toxicity (of any duration) Febrile neutropenia (ANC < 1.0 x 10 ⁹ /L or 1000/mm ³ and a single temperature of >38.3 °C (101 °F) or a sustained temperature of ≥38 °C (100.4 °F) for more than one hour.
Renal	Serum creatinine ≥ grade 3 (≥3.0 x baseline or >3.0 - 6.0 x ULN)
Hepatic	≥ CTCAE grade 3 total bilirubin (> 3 x ULN) AST or ALT grade 3 (>5.0 -20.0 x ULN) for ≥ 7 consecutive days AST or ALT grade 4 (>20.0 x ULN) Reactivation of Hepatitis B or/and C
Pancreas	Asymptomatic ≥ CTCAE grade 3 serum amylase or lipase (>2.0 × ULN) occurring for > 14 consecutive days Symptomatic serum amylase or lipase elevation, medical intervention required
Neurologic	Any neurological abnormality or toxicity ≥ grade 2
Cardiac	≥ CTCAE grade 3

Toxicity	Any of the following criteria:
Other AEs	Any other AE \geq grade 3 Grade 3 fatigue, lasting for > 7 consecutive days Grade 3 nausea, vomiting, diarrhea if in setting of optimal, anti-emetic and anti-diarrheal therapy
CTCAE version 4.03 will be used for all grading. Patients may receive supportive care (e.g. transfusion of red blood cells) as per local institutional guidelines.	

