6.2.5 Dose modification and delay

For patients who do not tolerate the protocol-specified dosing scheme, dose adjustments and interruptions are permitted. All dose modifications should be based on the worst preceding toxicity (CTCAE version 4.03). Once a dose reduction has occurred, the dose level may not be re-escalated during subsequent treatment cycles with INC280. In addition, in the Dose Determining Part, a patient must discontinue treatment with INC280 if, after treatment is resumed at a lower dose, the toxicity recurs with the same or worse severity. In the Dose Expansion Part, a patient must discontinue treatment with INC280 if, after treatment is resumed at the lowest allowed dose (200 mg BID, tablet), the toxicity recurs with the same or worse severity. All interruptions or modifications to study drug administration must be recorded on the Dose Administration Record eCRF.

If a dose delay of >21 days is required, then the investigational treatment with INC280 must be discontinued. [Table 6-3](#), [Table 6-4](#), [Table 6-5](#), [Table 6-7](#) and [Table 6-8](#) provide the guidelines to be followed for dose modification of the study drug in the event of toxicities. Included are

also instructions for re-initiation of study treatment once sufficient recovery of toxicity is seen. **Any dosing modifications that are not in accordance with the guidelines in Table 6-3, Table 6-4, Table 6-5, Table 6-7 and Table 6-8 (Andrew et al 2010) must be discussed with Novartis.** Any dose change to the study drug must be recorded on the eCRF. The study visit schedule should be followed irrespective of any study drug interruption.

In exceptional situations, study treatment may continue even if there is a dose interruption of >21 days or the patient experienced disease progression. The decision to allow for continuation of treatment will be made on a case-by-case basis following discussion between Novartis and the investigator. Situations that may allow for continuation of treatment include the following:

- A dose delay of >21 days has occurred but the patient is clearly benefiting from study treatment (i.e., SD, PR, or CR) and it is the investigator's opinion that no safety concerns are present.

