Febrile neutropenia ANC < 1.0 x 10 ⁹ /L or 1000/mm ³ and a single temperature of >38.3°C (101 °F) or a sustained temperature of >=38 °C (100.4 ° F) for more than one hour.	Discontinue dose until resolved, then: If resolved in ≤ 7 days, then resume treatment at ↓ 1 dose level. If resolved in > 7 days, then discontinue dose and patient from study treatment
Platelet count decreased (Thrombocytopenia) Grade 1 or 2 (< LLN – 50x10 ⁹ /L) Grade 3 (<50 – 25x10 ⁹ /L) Grade 4 (<25x10 ⁹ /L)	Maintain dose level Discontinue dose until resolved to ≤ grade 1 or baseline, then: If resolved in ≤7 days, then maintain dose level If resolved in > 7 days, then ↓ 1 dose level Discontinue dose until resolved to ≤ grade 1 or baseline, then ↓ 1 dose level
Renal	
Serum creatinine Grade 1 (> ULN – 1.5 x ULN) Grade 2 (> 1.5 - 3.0 x ULN) Grade 3 or 4 (> 3.0 x ULN)	Maintain dose level Discontinue dose until resolved to ≤ grade 1 or baseline, then maintain dose level. Patients will be instructed to increase their fluid intake until resolution to ≤ grade 1 or baseline. Discontinue dose until resolved to ≤ grade 1 or baseline, then resume treatment at ↓ 1 dose level. Patients will be instructed to increase their fluid intake until resolution to ≤ grade 1 or baseline. If grade 4 event recurs at any point during participation, discontinue study treatment.

Recommended dose modifications of INC280	
Worst toxicity CTCAE v4.03 grade	Recommended dose modifications any time during a cycle of therapy, including intended day of dosing
Hepatic	
Isolated Total Bilirubin ^a	
Grade 1 (> ULN – 1.5 x ULN)	Maintain dose level with liver function tests (LFTs)* monitored
Grade 2 (>1.5 - 3.0 x ULN)	Omit/delay dose until resolved to ≤ grade 1 or baseline, then: If resolved in ≤ 7 days, maintain dose level If resolved in > 7 days, ↓ 1 dose level
Grade 3 (> 3.0 - 10.0 x ULN)	Omit/delay dose until resolved to ≤ grade 1 or baseline, then: If resolved in ≤ 7 days, ↓ 1 dose level If resolved in > 7 days, discontinue patient from study treatment
Grade 4 (> 10.0 x ULN)	Discontinue dose and patient from study treatment.
Isolated AST or ALT	
Grade 1 or 2 (> ULN - 5.0 x ULN)	Maintain dose level with liver function tests (LFTs)* monitored
Grade 3 (> 5.0 – 20.0 x ULN)	Omit/delay until resolved to ≤ grade 1 or ≤ grade 2 if grade 2 elevation at baseline, then: If resolved in ≤ 7 days, maintain dose level of INC280 If resolved in > 7 days, ↓ 1 dose level of INC280 Discontinue dose and patient from study treatment.

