Renal	If serum creatinine \geq CTCAE grade 2 has been demonstrated, this parameter must be repeated at least twice a week until resolution to \leq CTCAE grade 1 or baseline, and then at least weekly until either initiation of re-treatment or until stabilization. Patients will be instructed to increase hydration until resolution to \leq CTCAE grade 1 or baseline.
Hepatic	In case of isolated elevations in total bilirubin, AST or ALT, additional follow-up evaluations are recommended as outlined in Table 6-9 .
Pancreatic	If serum amylase or serum lipase \geq CTCAE grade 3, follow until resolution to grade 2 or less.
Neurologic	If any neurological abnormality or toxicity \geq grade 2 has been demonstrated, neurological assessments must be repeated at least twice a week until resolution to \leq CTCAE grade 1. Unscheduled MRI and gadolinium enhanced T1 imaging may also be conducted to evaluate patients for intramyelinic edema like lesions, brain metastases and other unanticipated CNS occurrences. An EEG may also be performed to monitor for physiological changes in brain activity.
Cardiac	Monitor toxicity until resolution to grade 1 or baseline. If applicable, monitor electrocardiograms (ECGs) twice weekly until normalization or stabilization.
Non-laboratory	Patients who experience non-laboratory DLTs must be evaluated at least once a week following demonstration of the toxicity until resolution of the toxicity to allow for re-treatment, until stabilization of the toxicity, or until study completion.

Table 6-7 Guidelines for the management of hepatitis B reactivation

HBV-DNA OR HBsAg in baseline result	Definition of reactivation	Treatment
+	Increase of 1 log in HBV-DNA relative to baseline HBV- DNA value	
Provide antivirus treatment *
 
AND
 
Interrupt study drug administration until: ≤ baseline HBV-DNA levels
 
If resolution occurs within ≤ 21 days, study drug should be restarted at one dose lower, if available (see Table 6-2 and Table 6-3 for dose level available).
 
If the patient is already receiving the lowest dose of study drug according to the protocol, the patient should restart at the same dose after resolution.
 
If resolution occurs >21 days, patients should discontinue study drug but continue antiviral therapies at least 4 weeks after last dose of study drug.

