7.2.2.5 Laboratory evaluations

The local site laboratory will be used for the following standard clinical laboratory assessments: hematology, chemistry, coagulation, urinalysis and serum pregnancy test. All analyses for these tests will be performed locally and the results will be based on local laboratory normal ranges. Creatinine clearance will be calculated using Cockcroft-Gault formulation for Glomerular Filtration Rate (GFR) estimation ([Appendix 6](#)).

Table 7-4 Local clinical laboratory parameters collection plan

Test Category	Test Name
Hematology	Complete blood count, including total White blood cells (WBC) with differentials (neutrophil count), hemoglobin (Hb), hematocrit, platelet count.
Chemistry	Albumin, ALP, ALT (SGPT), AST (SGOT), Amylase, Bicarbonate, Calcium, Chloride, Creatinine, glucose, lipase, inorganic phosphorus, magnesium, potassium, sodium, Direct Bilirubin, Total Bilirubin, Total Cholesterol, Total Protein, Triglycerides, Blood Urea Nitrogen (BUN) or Urea, Uric Acid.
Urinalysis	Macroscopic Panel (Dipstick) (Bilirubin, Blood, Glucose, Ketones, Leukocytes esterase, Nitrite, pH, Protein, Specific Gravity, Urobilinogen) Microscopic Panel (Red Blood Cells, WBC, Casts, Crystals, Bacteria, Epithelial cells)
Coagulation	Prothrombin time (PT) or International normalized ratio (INR)
Hepatitis markers	HBV-DNA, HBsAg, HBcAb, HBsAb, HCV RNA-PCR
Tests for hepatotoxicity follow-up (if clinically indicated for INC280)	LFTs: albumin, ALT, AST, GGT, total bilirubin, direct and indirect bilirubin, ALP, ALP fractionated (quantification of isoforms) Creatine kinase, prothrombin time (PT)/INR Testing for acute hepatitis A, B, C or E infection, other hepatotropic viral infection and autoimmune hepatitis as clinically indicated (refer to Section 6.2.6.1)

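### Tables 6-2 and 6-5 of the protocol both invoke CTCAE 4.03 but grade creatinine differently, so a threefold rise from a baseline at or below ULN is grade 3 in one and grade 2, grade 1 or ungraded in the other

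*Protocol*

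**What the plan says.** **Table 6-2 (Protocol Section 6.2.3)** lists the events that enter the dose decision analysis. The renal row reads "Serum creatinine ≥ grade 3 (≥3.0 x baseline or >3.0 - 6.0 x ULN". One criterion is enough: the event qualifies if it is judged drug-related and "meets any of the criteria in" the table. The baseline route has no minimum multiple of ULN. The table note says "CTCAE version 4.03 will be used for all grading".

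**Table 6-5 (Protocol Section 6.2.5)** sets the dosing action. Its creatinine bands are "Grade 1 (> ULN – 1.5 x ULN"), then "Grade 2 (> 1.5 - 3.0 x ULN) Grade 3 or 4 (> 3.0 x ULN"). The actions are to keep the dose at grade 1, interrupt and resume at the same level at grade 2, and interrupt and resume one level lower at grade 3 or 4. Baseline appears only as a recovery target, never as a grading criterion. The column is headed with CTCAE v4.03, and the section text says "All dose modifications should be based on the worst preceding toxicity (CTCAE version 4.03").

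**Table 6-6 (same section)** requires creatinine to be repeated at least twice weekly from CTCAE grade 2 upwards. It prints no threshold of its own.

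**Exclusion criterion 23 (Section 5.3)** caps entry creatinine at 1.5 x ULN and sets no lower limit, so low baselines are eligible.

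**The concern.** One laboratory value receives two grades under one named version of one grading system. A site that follows the printed bands of Table 6-5 can assign a low grade, or none, to a rise that Table 6-2 calls grade 3. A site that applies the baseline route instead departs from the printed bands, and Section 6.2.5 requires dosing changes outside its tables to be discussed with the sponsor. Sites can reasonably differ.

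The choice has consequences. It decides whether drug is interrupted, at what level it resumes, and whether the twice-weekly repeats start. Under the reduced schedule in Table 7-2, routine biochemistry is every 12 weeks, so an event below grade 2 may not bring another protocol-required creatinine for that long.

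Renal safety matters in this trial. Section 1.2.1.1.3 names the kidney as a target organ, with crystalline-like deposits in the 28-day monkey study, although the 13-week study found no kidney toxicity up to 75 mg/kg/day. The Amendment 2 rationale says creatinine clearance was added because some patients in this study had raised creatinine or renal failure.

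**Working it through.** The plan states no figure to reproduce. The check maps one set of thresholds onto the other.

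**Inputs**
- Table 6-2, grade 3 or higher: value ≥ 3.0 x baseline, or > 3.0 x ULN.
- Table 6-5: grade 1 is > 1.0 to 1.5 x ULN, grade 2 is > 1.5 to 3.0 x ULN, grade 3 or 4 is > 3.0 x ULN.
- Baseline *b*, in multiples of ULN; entry cap *b* ≤ 1.5.

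**Step 1: a rise of exactly threefold.** The new value is 3*b*, which always qualifies in Table 6-2. The Table 6-5 boundaries fall where:
- 3*b* = 1.0, so *b* = 1/3 (0.333)
- 3*b* = 1.5, so *b* = 0.50
- 3*b* = 3.0, so *b* = 1.0

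| Baseline (x ULN) | Value after threefold rise (x ULN) | Table 6-2 | Table 6-5 |
|---|---|---|---|
| ≤ 0.333 (e.g. 0.30) | ≤ 1.0 (0.90) | Grade 3 | Ungraded |
| > 0.333 to 0.50 (e.g. 0.40; 0.50) | > 1.0 to 1.5 (1.20; 1.50) | Grade 3 | Grade 1: keep the dose |
| > 0.50 to 1.0 (e.g. 0.51; 1.00) | > 1.5 to 3.0 (1.53; 3.00) | Grade 3 | Grade 2: interrupt, resume same dose |
| > 1.0 to 1.5 (e.g. 1.01; 1.50) | > 3.0 to 4.5 (3.03; 4.50) | Grade 3 | Grade 3 or 4: interrupt, resume one level lower |

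**Step 2: larger rises.** For *b* ≤ 1.0 the grades differ for every value from 3*b* up to 3.0 x ULN. At *b* = 0.50, Table 6-5 reaches grade 3 only above 3.0/0.50 = 6 times baseline. At *b* = 0.40, it stays at grade 1 up to 1.5/0.40 = 3.75 times baseline.

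**Step 3: direction.** Any value above 3.0 x ULN is at least grade 3 in both tables. The mismatch therefore runs one way, with Table 6-5 giving the lower grade.

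**Step 4: comparison with other rows.** The grade 3 cut-points for bilirubin (> 3 x ULN), AST/ALT (> 5 to 20 x ULN) and amylase/lipase (> 2 x ULN) match across the two tables. Creatinine does not.

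**The case against.** **Different jobs.** Table 6-2 counts events and Table 6-5 directs dosing, and a stricter threshold for counting than for acting is an ordinary design choice. That would answer the point if the protocol said so. It does not: both tables attach a grade from the same CTCAE version to the same value, and the other laboratory cut-points above agree.

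**CTCAE governs.** Section 6.2.5 and the Table 6-5 heading defer to CTCAE 4.03, so the ULN bands could be read as shorthand. This is a possible reading, but the table prints explicit bands and nothing says that another criterion overrides them.

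**Discretion remains.** Table 6-5 is titled as recommended guidance, and toxicity or physician decision can end treatment. This stands: no site is forced to continue dosing. It does not settle the grade.

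A reader might also infer more than the documents support:
- *That any threefold rise from a normal baseline is dosed through.* Above 0.50 x ULN, Table 6-5 interrupts drug.
- *That the expansion dose was miscounted.* Appendix 5, Table 14-18, does show one event in six moving the model recommendation from 600 to 500 mg bid. But the documents do not report that a creatinine event was missed, and the Amendment 2 study update shows that part complete.
- *That Table 6-6 is a third conflicting definition.* It prints none; it inherits the ambiguity.
- *That the rise can be converted into a clearance loss and compared with the 45 mL/min entry floor.* Appendix 6 lists its formula for stable kidney function and uses lean body mass, so it does not fit a threefold rise.

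**Conclusion.** The contradiction stands. For a threefold rise it covers every baseline at or below ULN: grade 3 against grade 2 in the wider band (above 0.50 to 1.0 x ULN), grade 3 against grade 1 in the narrower band (above 0.333 to 0.50 x ULN), and grade 3 against no grade at or below 0.333 x ULN. Only the last two carry no instruction in Table 6-5 to interrupt drug.

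The Table 6-2 count applied to related events in the first 28 days of a completed part, and the SAP introduction records that enrolment stopped permanently after 25-Dec-2016, so that effect is historical. The continuing effect is on dose-modification grading and the Table 6-6 trigger for patients still on drug. Amendment 6 provides for such patients but does not say how many there are.

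The conclusion rests on the printed thresholds and on finding no precedence rule. The documents give no distribution of baseline creatinine, so the frequency of such events is unknown.

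**What to change.** Reconcile the creatinine rows of Tables 6-2 and 6-5 in one of two ways:

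1. Put both under one stated grade definition, chosen by the clinical team.
2. State that the counting and acting thresholds differ on purpose, and remove the shared grade label so that one value no longer carries two grades.

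In either case, say which grade triggers the twice-weekly repeats in Table 6-6. This review takes no position on which definition is right.

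The cost is a table edit in an amendment or an investigator letter. Baseline creatinine is already collected, so no new baseline test is needed. Depending on the definition chosen, there may be a few more interruptions and repeat tests.
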